ETV: entecavir; ID: identification; IMP: Investigational Medicinal Product; JNJ 3989: JNJ 73763989; NA: nucleos(t)ide analog; NIMP: Non investigational Medicinal Product; Q4W: once every 4 weeks; qd: once daily; TAF: tenofovir alafenamide

^a In countries where TAF is commercially available, it will be one of the NA treatment options.

^b 2 tablets of 0.5 mg

EFFICACY EVALUATIONS

HDV RNA will be quantified at central testing laboratory locations (China versus outside of China) using a validated commercially available in vitro nucleic acid amplification tests for the quantification of HDV RNA. Samples may be processed in real-time or could be analyzed in batch.

Qualitative and quantitative HBsAg and HBeAg, and quantitative HBcrAg as well as anti-hepatitis B surface (HBs) and anti-hepatitis B e (Hbe) antibodies will be determined using standard commercially available serologic assays in a central laboratory. Samples for the determination of HBsAg and HBeAg will be processed in real-time. Samples for the determination of HBcrAg can be analyzed in batch and at the sponsor's discretion.

HBV DNA will be quantified at central laboratories using commercially available in vitro nucleic acid amplification tests for the quantification of HBV DNA. Samples for the determination of HBV DNA will be processed in real-time. HBV RNA will be quantified using a validated assay in a central laboratory. Samples for the determination of HBV RNA can be analyzed in batch and at the sponsor's discretion.

Liver stiffness measurement by VCTE (FibroScan) will be performed to determine changes in the liver fibrosis.

Samples may be used by the sponsor for additional exploratory assessments analyzing the serologic and virologic characteristics of HBV or HDV infection (including semi-quantitative anti-HDV IgM antibodies) and efficacy or safety of the study intervention.

Sequencing

Viral genome sequence analysis may be performed to identify pre-existing baseline polymorphisms and to evaluate emergence of mutations associated with JNJ-3989 and/or NA treatment.

Core Liver Biopsy and Fine Needle Aspirate Biopsy (Optional with Separate Consent, Part 2 only)

If participants agree to undergo an optional liver biopsy, percutaneous core liver biopsies and/or fine needle aspirate biopsies (FNABs) will be performed preferentially at Week 0 and Week 24. Percutaneous core liver biopsies will be prioritized over FNAB if only one sample can be collected.

SAFETY EVALUATIONS

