Safety and tolerability will be assessed throughout the study from the time that the informed consent form (ICF) is signed until completion of the last study-related activity, which may include contact for follow-up of safety. The evaluations of safety and tolerability will include monitoring of (S)AEs, physical examinations, vital signs measurements (including body weight), triplicate 12-lead ECGs, and clinical laboratory tests (including hematology, blood biochemistry, blood coagulation, urinalysis, urine chemistry, and renal biomarkers).

Any clinically relevant changes occurring during the study must be recorded in the AE section of the case report form.

Adverse events of special interest in line with the known pharmacological profile of the study intervention (and the drug classes) evaluated in this study are implemented.

Any intervention-emergent elevation of ALT and/or AST $\geq 3x$ ULN and $\geq 2x$ nadir (ie, lowest value during study participation) should trigger an assessment of confounding factors (alcohol intake, change in concomitant medication, and comorbidities) and should trigger a confirmatory study visit to repeat laboratory testing as specified below. Repeat laboratory values should include AFP, ALT, AST, ALP, bilirubin (total and direct), INR, albumin, HBV DNA, and HDV RNA. Additional tests should be considered based on clinical judgement. The confirmatory visit should be scheduled preferably within 3 days of the receipt of the initial ALT/AST results.

Weekly basis monitoring (or more frequently as long as values increase) until ALT/AST levels have returned to $< 3x$ ULN or $< 2x$ nadir, and if present, liver-related symptoms have improved. With ALT and/or AST values $\geq 3x$ ULN and $\geq 2x$ nadir, visit intervals may be extended to 14 days if values have been stable or decreasing on three consecutive visits. The participant will be monitored (laboratory testing of ALT, AST, ALP, bilirubin [total and direct], INR, albumin, HBV DNA, and HDV RNA) on a weekly basis or more frequently until ALT and/or AST levels have returned to 50% of the maximal value.

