- NA treatment will continue for all study participants until the last study visit (FU W48). Only for non-cirrhotic participants, NA treatment can be discontinued during the follow-up phase in case of a confirmed HBsAg seroclearance, ALT <3x ULN, and HBV DNA <LLOQ. Amongst the non-cirrhotic participants who discontinue treatment with NA, NA treatment will be restarted if any of the criteria listed in Section 6.5 are met.
- A liver ultrasound is performed approximately every 24 weeks from start of open-label phase for HCC screening in all participants. A window of 1 week is allowed before or after the scheduled visit. In case MRI monitoring is used per patient's standard of care, these MRI results may also be used.
- Complete physical examination, including height (at screening only), skin examination, and other body systems.
- Symptom-directed physical examination.
- Vital signs include supine SBP, DBP, pulse rate, body weight, and body temperature.
- All ECGs will be read centrally.
- All injection site reactions (ISRs; including ISRs below grade 1) will need to be recorded in the special events section of the CRF.
- Biochemistry samples must be taken after fasting for at least 10 hours for measurement of phosphate, calcium, creatinine, and lipids.
- Creatinine clearance (eGFR calculated by the CKD-EPI formula) will be assessed.

- m. Intervention-emergent ALT/AST elevations (ie, ALT and/or AST ≥ 3 x ULN and ≥ 2 x nadir [ie, lowest value during study participation]), should trigger an assessment of confounding factors (alcohol intake, change in concomitant medication, and comorbidities) and a confirmatory visit, to be scheduled preferably within 3 days of the receipt of the initial ALT/AST results, to repeat laboratory testing of AFP, ALT, AST, ALP, bilirubin (total and direct), INR, albumin, HBV DNA, and HDV RNA. Note that in case of urgency, local laboratory assessments could be considered. (except for HDV RNA and HBsAg to protect the blind) Off-treatment local HDV RNA test can be done to exclude/assess for HDV driven flare. Additional tests should be considered based on clinical judgement. For more details and further management guidance refer to Section 8.3.6.1, Intervention-emergent ALT/AST Elevations and Section 10.6, Appendix 6: Intervention-emergent ALT/AST Elevations.
- n. Only applicable to participants who are enrolled at a site with an access to a FibroScan device.

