6.3. Measures to Minimize Bias: Randomization and Blinding

Intervention Allocation

Procedures for Randomization and Stratification

Central randomization will be implemented in this study. Participants will be randomly assigned to 1 of 2 intervention arms of each part of the study with ratio 4:1 (JNJ-3989 + NA: placebo + NA) based on a computer-generated randomization schedule prepared before the study by or under the supervision of the sponsor.

The randomization will be balanced by using randomly permuted blocks and will be stratified by the presence of compensated cirrhosis at screening (yes or no, Part 1 only), HDV RNA testing laboratory location (China versus outside of China), and HBeAg status at screening (positive versus negative). The IWRS will assign a unique intervention code, which will dictate the intervention assignment and matching study intervention kit for the participant. The requestor must use his or her own user identification and personal identification number when contacting the IWRS, and will then give the relevant participant details to uniquely identify the participant.

Blinding

Blinded treatment will be used to reduce potential bias during data collection and evaluation of clinical endpoints.

The investigators, participants, and all site personnel will remain blinded to study intervention allocation until a participant has completed the Week 48 visit or has discontinued earlier. When a participant has completed the Week 48 visit or discontinued earlier, the investigator, site personnel, sponsor, and participants will be unblinded for treatment allocation and all laboratory data, including HDV RNA and HBsAg data. After Week 48, it will be communicated to the investigators whether the participant was allocated to either the immediate active arm (Arm 1) or the deferred active arm (Arm 2) to allow that the participant follows the correct visit schedule during the open-label phase (see Section 1.3.2, Schedule of Activities – Open-label Study Intervention Phase (Weeks 52 – EOT)).

As of Week 52 and up and until the end of the study intervention phase, study intervention will be administered in open-label fashion to all participants and efficacy results (eg, HDV RNA and HBsAg data) will be reported to the sites.

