8.1. Efficacy Assessments

Efficacy assessments will be performed at the time points indicated in the [Schedule of Activities](#).

HDV RNA will be quantified at central testing laboratory locations (China versus outside of China) using a validated commercially available in vitro nucleic acid amplification tests for the quantification of HDV RNA. Samples may be processed in real-time or could be analyzed in batch.

Qualitative and quantitative HBsAg and HBeAg, and quantitative HBcrAg as well as anti-hepatitis B surface (HBs) and anti-hepatitis B e (Hbe) antibodies will be determined using standard commercially available serologic assays in a central laboratory. Samples for the determination of HBsAg and HBeAg will be processed in real-time. Samples for the determination of HBcrAg can be analyzed in batch and at the sponsor's discretion.

HBV DNA will be quantified at central laboratories using commercially available in vitro nucleic acid amplification tests for the quantification of HBV DNA. Samples for the determination of HBV DNA will be processed in real-time. HBV RNA will be quantified using a validated assay in a central laboratory. Samples for the determination of HBV RNA can be analyzed in batch and at the sponsor's discretion.

HBV DNA results will be provided to the investigator and the sponsor from screening until the end of follow-up.

It is the responsibility of the investigator:

- To monitor HBV DNA results and ensure that investigational intervention is discontinued in participants with virologic breakthrough (see Section 7.1).

For each participant, the post-baseline HDV RNA, HBsAg, HBeAg, HBcrAg, anti-HBs, and anti-Hbe antibody testing results from the Week 52 visit onwards will be provided to the investigator for managing the participant's safety. For Part 1, the sponsor will be unblinded to Part 1 data from the moment of data unblinding for Part 1 IA1 onwards. For Part 2, the sponsor will be blinded until the Week 52 visit. For safety-related decisions, Part 1 HDV RNA and HBsAg data may be discussed with investigators on a case-by-case basis. When a participant has completed the Week 48 visit or discontinued earlier, the investigator, site personnel, sponsor, and participant will be unblinded for treatment allocation and all laboratory data, including HDV RNA and HBsAg data.

Liver stiffness measurements will be performed by VCTE (FibroScan) to determine changes in the liver fibrosis.^{1,4}

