9.5. Interim Analyses

9.5.1. Interim Analyses of Study Part 1

During the double-blind phase of Part 1, 2 IAs will be conducted by the sponsor.

Part 1 IA1: One IA will be conducted after all participants of Part 1 have completed at least Week 16 (or discontinued earlier) to allow a comprehensive review of ALT elevations observed during treatment. An in-depth understanding of the kinetics of virological parameters (eg, HDV RNA, HBsAg, HBV DNA, etc) is critical to interpret the observed ALT elevations and their pattern over time, in light of preliminary understanding the benefit-risk ratio of the investigational regimen in HDV-infected participants. The sponsor will become unblinded to Part 1 efficacy and safety data for this IA to inform the decision of the Sponsor Committee for the initiation of Part 2 in conjunction with the IDMC recommendations.

From the moment of data unblinding for Part 1 IA1 onwards, the sponsor will remain unblinded to Part 1 data. The investigators, participants, site personnel, and operational sponsor team members involved with the sites will remain blinded. For safety-related decisions, HDV RNA and HBsAg data may be discussed with investigators on a case-by-case basis.

Part 1 IA2: A second IA will be conducted after all participants of Part 1 have completed at least Week 48 visit (or discontinued earlier).

9.5.2. Interim Analysis of Study Part 2

The original protocol included an IA of Part 2 when all participants had reached Week 148 (EOT or discontinued earlier). This IA of Part 2 was to be conducted to assess safety and evaluate the time course of different disease markers and to support the sponsor's interactions with health authorities. Due to the decision to reduce the study duration of Part 2 and since interactions with health authorities are no longer planned, the IA of Part 2 was removed per Protocol Amendment 5.

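### Open-label schedule footnotes bar urgent local HDV RNA and HBsAg tests in an on-treatment flare to protect a blind that has already ended

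*Protocol*

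**What the plan says.** **Flare work-up.** The Synopsis and Section 8.3.6.1 define the panel: "Repeat laboratory values should include AFP, ALT, AST, ALP, bilirubin (total and direct), INR, albumin, HBV DNA, and HDV RNA". On timing: "The confirmatory visit should be scheduled preferably within 3 days of the receipt of the initial ALT/AST results". Weekly monitoring follows, again with HDV RNA, and may be stretched to 14 days when values are stable or falling.

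**Local tests in the open-label schedules.** Footnote m of Section 1.3.2.1 (before Amendment 5) and of Section 1.3.2.2 (per Amendment 5) allows urgent local tests, "except for HDV RNA and HBsAg to protect the blind". The next sentence permits a local HDV RNA test once the participant is off treatment. The follow-up footnotes (j in 1.3.3.1, k in 1.3.3.2) and the double-blind footnote (u in 1.3.1) carry the same exception.

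**Local tests elsewhere.** Sections 6.3 and 8.1 prohibit local HDV RNA and HBsAg tests during blinded treatment only. The Synopsis and Section 8.3.6.1 allow urgent local assessments without the exception. Section 10.10.1 (COVID-19 disruption) prohibits these local tests throughout the study intervention phase, unless the sponsor instructs otherwise.

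**Access to results.** Section 6.3 states that from Week 52 "efficacy results (eg, HDV RNA and HBsAg data) will be reported to the sites". Section 8.1 says results "from the Week 52 visit onwards will be provided to the investigator for managing the" participant's safety.

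**Central processing.** For HDV RNA: "Samples may be processed in real-time or could be analyzed in batch". For HBV DNA: "Samples for the determination of HBV DNA will be processed in real-time". Section 8.1 repeats both sentences.

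**The concern.** A site managing an on-treatment flare in the open-label phase finds two answers in one document. The schedule footnote, which is what site staff work from, refuses a local HDV RNA test. The body text allows it. The only reason given for refusing is protection of a blind that no longer exists for that participant.

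ALT elevation is the important potential risk of JNJ-3989, and Section 2.3.1.2 describes a sustained pattern in Parts 1 and 2 whose mechanism is not understood. Whether a flare is driven by HDV is a question the protocol itself wants answered, since it permits local HDV RNA testing for that purpose off treatment. At stake is how soon that answer is available for a participant still being dosed. It could inform the investigator's discretionary decision to stop for safety (Section 7.1) and the Data Review Committee's (DRC) flare review (Section 9.5.4).

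**Working it through.** No power, rate or effect size is involved. The check sets the texts side by side.

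1. **Is there a blind to protect?** No. Section 6.3 unblinds each participant's allocation and laboratory data once Week 48 is completed or the participant discontinues earlier. Sections 4.1 and 6.3 state that all data are unblinded in the open-label phase. The Amendment 5 rationale says every participant in both parts was already beyond the double-blind phase. The Section 1.3.2.2 schedule was added by that amendment, so the reason given in its footnote could apply to nobody.

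2. **Does the body text support the ban?** No. Sections 6.3 and 8.1 confine it to blinded treatment. The Synopsis and Section 8.3.6.1 carry no exception for HDV RNA or HBsAg.

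3. **Does the off-treatment permission rescue the footnote?** Not for a participant still on JNJ-3989. Under Amendment 5, Part 2 dosing continues until an end-of-treatment visit no earlier than Week 96 (Arm 1) or Week 100 (Arm 2). A flare before that visit is on treatment.

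4. **Which marker matters in practice?** HDV RNA is in the flare panel. HBsAg is not on that list, so the practical effect is mainly on HDV RNA.

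5. **Who is concerned?** Part 2 status in the Amendment 5 rationale: 11 completed + 17 open-label + 2 in follow-up = 30. Open-label share: 17/30 = 56.7%. All 22 Part 1 participants had finished investigational treatment. The figure of 17 is an upper bound at the time of writing, because participants leave the group at their end-of-treatment visit.

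6. **Do defined decisions depend on HDV RNA?** No. The JNJ-3989 stopping criteria for flares in Section 8.3.6.1 use ALT/AST level and duration, INR, direct bilirubin, albumin, symptoms and other signs of reduced liver function. The NA-restart criteria in Section 6.5.1 use liver function, HBeAg, HBV DNA and ALT.

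7. **Can the delay be sized?** No. The protocol gives neither a batch interval nor a turnaround time. The only yardstick is the weekly flare visit: a wait above 7 days would let at least one such visit pass without the previous HDV RNA result. Whether that happens is unknown.

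8. **Other places with the same wording.** Follow-up footnotes j and k state the exception and then allow off-treatment local HDV RNA testing, so they contradict themselves but leave access open. Section 10.10.1 gives maintenance of blinding as its purpose but applies the ban to the whole intervention phase. The Synopsis describes that phase as 52 double-blind weeks followed by open-label treatment.

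**The case against.** The strongest case is that this is an editorial leftover. The footnote sends readers to Section 8.3.6.1 for management guidance, and that section is permissive. The group is small and shrinking: once Amendment 5 is in effect, anyone past Week 96 or Week 100 stops at the next planned visit and is then off treatment, where local HDV RNA is expressly allowed. Footnote m of 1.3.2.1 loses its population once the amendment is effective. Some sites do not run HDV tests as standard of care, so a local test may not be available. All of this stands and limits the weight of the point. It does not remove the conflict for participants still being dosed, because the current schedule tells sites the opposite of the body text.

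Four stronger readings are tempting, and the documents do not support them.

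- *The batching sentence is an error.* It permits either mode and tells no laboratory to hold a flare sample. Sample handling is left to the Laboratory Manual, which is not shown and may set a turnaround.
- *Section 9.5.1 demands real-time results for each flare because viral kinetics* "is critical to interpret the observed ALT elevations and their pattern over time". That text explains the first Part 1 interim analysis, a review of accumulated data. It does not address turnaround for an individual flare.
- *Stopping of JNJ-3989 or restarting of NA would be late.* No such rule uses HDV RNA. The DRC meets periodically, so its review does not establish a need for same-week results either.
- *17 of 30 participants are affected.* They were in the open-label phase when the amendment was written. Only those still dosing who have an urgent flare are exposed, and their flare rate is not given.

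**Conclusion.** The contradiction is established from the text and needs no assumption: the open-label footnotes bar a local test for a reason that has lapsed, against Sections 4.1, 6.3, 8.1 and 8.3.6.1. It is more than clerical, because it is an operative site instruction about a known on-treatment liver risk.

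Its size is modest. It can affect how quickly an on-treatment flare is interpreted in participants still receiving open-label JNJ-3989, at most 17 of 30 (56.7%) in Part 2 when Amendment 5 was written. No protocol-defined stopping or NA-restart rule is affected, no endpoint or analysis changes, and the delay cannot be quantified. Any practical gain assumes that a site has a local HDV RNA test available and that the central result would not arrive sooner.

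The change should be made because it is cheap and could speed the work-up of a flare. The lack of a real-time requirement for flare samples is a secondary point, an improvement and not the correction of an error.

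**What to change.** **Main change.**
- Delete the parenthetical exception from footnote m in Sections 1.3.2.2 and 1.3.2.1. For consistency, also delete it from follow-up footnotes j (1.3.3.1) and k (1.3.3.2). Keep it in double-blind footnote u (1.3.1), where it belongs.
- In the sentence that follows it in those footnotes, extend the permission for local HDV RNA testing so that it covers open-label as well as off-treatment participants.
- In Section 10.10.1, limit the ban on local tests to the double-blind part of the intervention phase.

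**Secondary change.** In the Synopsis efficacy evaluations and Section 8.1, state that HDV RNA samples from flare confirmatory and flare-monitoring visits are run in real time, while other samples may be batched.

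**Cost.** One deleted phrase and one widened sentence in four footnotes, one narrowed phrase in the appendix, one added condition in two places, and a matching line in the Laboratory Manual. The edits need the usual ethics committee approval for an amendment (Section 10.3.1). The running cost is a slightly higher assay cost for a few flare samples.

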1.2. Schema

Figure 1: Schematic Overview of the Study

FU: follow-up; JNJ-3989: JNJ-73763989; n: number of participants; NA: nucleos(t)ide analog

* The antiviral activity assessments monitored in Part 1 of the study are described in Section 8.1.1.

indicates the end of the intervention phase with JNJ-3989 treatment up until minimum Week 96 (Arm 1) and minimum Week 100 (Arm 2) in Part 2 per Protocol Amendment 5. Participants who stop treatment with JNJ-3989 after Protocol Amendment 5 will enter a 24-week FU phase.

1.3. Schedule of Activities

1.3.1. Schedule of Activities – Screening and Double-blind Study Intervention Phase (First 48 Weeks)

The Schedule of Activities (SoA) from screening to double-blind study intervention phase is the same for both Part 1 and Part 2 of the study, except for the liver biopsy samples which are scheduled only in Part 2 of the study.

Assessments from Week 52 until end of treatment (EOT) are described in Section 1.3.2, Schedule of Activities – Open-label Study Intervention Phase (Weeks 52 – EOT).

Study Phase	Screening	Double-Blind Study Intervention													
Week (W)	W 4 to 0 ^b	W0 ^c	W2	W4	W8	W12	W16	W20	W24	W28	W32	W36	W40	W44	W48/ WD ^a
Study Day (Window)	28	1	15 +/- 2d	29 +/- 2d	57 +/- 2d	85 +/- 2d	113 +/- 3d	141 +/- 3d	169 +/- 3d	197 +/- 3d	225 +/- 3d	253 +/- 3d	281 +/- 3d	309 +/- 3d	337 +/- 3d
Screening/Administrative															
ICF ^d	X														
ICF for optional liver biopsy ⁿⁿ	(X)														
Inclusion/exclusion criteria ^e	X														
Prestudy therapy (including prior anti HBV/HDV therapy)	X														
Medical/surgical history and demographics ^f	X														
Preplanned surgery/procedure(s)	X														
FibroScan or liver biopsy ^g	X														
HLA testing ^{kk}		X													
Abdominal ultrasound ^h	X														
Serum IgM anti HBc antibody test	X														
Serum anti HDV antibody test ^{oo}	X														
Testing for hepatitis A, B, C, and E virus, HIV 1 and 2	X														
AFP	X														
Hemoglobin A1c test	X														
FSH test (postmenopausal women only) ^k	X														
Serum pregnancy test (women of childbearing potential only)	X														

Study Phase	Screening	Double-Blind Study Intervention													
Week (W)	W 4 to 0 ^b	W0 ^c	W2	W4	W8	W12	W16	W20	W24	W28	W32	W36	W40	W44	W48/ WD ^a
Study Day (Window)	28	1	15 +/ 2d	29 +/ 2d	57 +/ 2d	85 +/ 2d	113 +/ 3d	141 +/ 3d	169 +/ 3d	197 +/ 3d	225 +/ 3d	253 +/ 3d	281 +/ 3d	309 +/ 3d	337 +/ 3d
Study Intervention Administration															
Randomization		X													
Administer JNJ 3989 (or placebo)		X		X	X	X	X	X	X	X	X	X	X	X	X
Dispense NA		X		X	X	X	X	X	X	X	X	X	X	X	X
Intake of NA ¹		X	X	X	X	X	X	X	X	X	X	X	X	X	X
NA accountability			X	X	X	X	X	X	X	X	X	X	X	X	X
Safety Evaluations															
Complete physical examination ^m	X								X						X
Symptom directed physical examination ^o		X	X	X	X	X	X	X		X	X	X	X	X	
Liver ultrasound ⁿ		X							X						X
Vital signs ^p	X	X	X	X	X	X	X	X	X	X	X	X	X	X	X
Triplicate 12 lead ECG ^q	X	X		X		X			X			X			X
Injection site reactions ^f		X	X	X	X	X	X	X	X	X	X	X	X	X	X
Clinical Laboratory Tests															
Hematology	X	X	X	X	X	X	X	X	X	X	X	X	X	X	X
Blood chemistry (including liver function tests) ^{s,t,u}	X	X	X	X	X	X	X	X	X	X	X	X	X	X	X
Blood coagulation	X	X	X	X	X	X	X	X	X	X	X	X	X	X	X
Urinalysis and urine chemistry ^v	X	X		X	X	X	X	X	X	X	X	X	X	X	X
Urine pregnancy test (women of childbearing potential only)		X		X	X	X	X	X	X	X	X	X	X	X	X
Renal biomarkers ^w		X				X			X			X			X
Efficacy Evaluations															
FibroScan ^y		(X) ^x													(X) ^{x,z}
HBV and HDV Virology															
HBV genotype ⁱ		X													
HDV genotype ^j		X													
Blood sampling for HDV RNA ^{aa}	X	X	X	X	X	X	X	X	X	X	X	X	X	X	X
Blood sampling for HBV DNA	X	X		X	X	X	X	X	X	X	X	X	X	X	X
Blood sampling for HBV RNA ^{bb}		X				X			X			X			X
Sampling for viral genome sequencing ^{cc}	X	X				X			X						X

Study Phase	Screening	Double-Blind Study Intervention													
Week (W)	W 4 to 0 ^b	W0 ^c	W2	W4	W8	W12	W16	W20	W24	W28	W32	W36	W40	W44	W48/ WD ^a
Study Day (Window)	28	1	15 +/ 2d	29 +/ 2d	57 +/ 2d	85 +/ 2d	113 +/ 3d	141 +/ 3d	169 +/ 3d	197 +/ 3d	225 +/ 3d	253 +/ 3d	281 +/ 3d	309 +/ 3d	337 +/ 3d
HBV and HDV Serology															
Blood sampling for:															
Anti HBs (quantitative) and anti HBe		X							X						X
HBsAg HBeAg (qualitative)	X														
HBeAg (qualitative)	X								X						X
HBsAg (quantitative)	X	X	X	X	X	X	X	X	X	X	X	X	X	X	X
HBeAg ^{dd} (quantitative)		X				X			X			X			X
HBcrAg ^{bb}		X				X			X			X			X
Exploratory serology ^{ee}	X	X				X			X			X			X
Pharmacokinetics															
Blood sampling for sparse PK of JNJ 3989 ^{ff}		X		X		X			X						X
Liver Biopsy (optional)^{gg}															
Percutaneous core liver biopsy sample		X ^{mm}							X ^{mm}						
FNAB		X ^{mm}							X ^{mm}						
Exploratory Biomarkers															
Antidrug antibodies (to JNJ 3989) ^{gg}		X							X						X
Immune Monitoring															
Immune cells (PBMCs) (selected sites only) ^{hh}		X													X
Pharmacogenomics (DNA)															
Exploratory host DNA genotyping (optional) ⁱⁱ		X													
Medical resource utilization ^{jj}	X	X	X	X	X	X	X	X	X	X	X	X	X	X	X
Ongoing Participant Review															
Concomitant therapy	X	X	X	X	X	X	X	X	X	X	X	X	X	X	X
Adverse events	X	X	X	X	X	X	X	X	X	X	X	X	X	X	X

General Note: The ECGs should preferably be completed before any tests, procedures or other consultations for that visit to prevent influencing the participant’s perceptions.

AFP: alpha-fetoprotein; ALP: alkaline phosphatase; ALT: alanine aminotransferase; AST: aspartate aminotransferase; CKD-EPI: Chronic Kidney Disease Epidemiology Collaboration; CRF: case report form; CT: computed tomography; D/d: Day/days; DBP: diastolic blood pressure; DNA: deoxyribonucleic acid; ECG: electrocardiogram; eGFR: estimated glomerular filtration rate; FSH: follicle-stimulating hormone; HBc: hepatitis B core protein; HBe(Ag): hepatitis B e (antigen); HBcrAg: hepatitis B core-related antigen; HBs(Ag): hepatitis B surface (antigen); HBV: hepatitis B virus; HCC: hepatocellular carcinoma; HDV: hepatitis D virus; HIV-1 (-2): human immunodeficiency virus type 1 (type 2); ICF: informed consent form; IgG: immunoglobulin G; IgM: immunoglobulin M; IWRS: interactive web response system;

JNJ-3989: JNJ-73763989; MRI: magnetic resonance imaging; NA: nucleos(t)ide analog; PBMC: peripheral blood mononuclear cells; PK: pharmacokinetic; RNA: ribonucleic acid; SBP: systolic blood pressure; ULN: upper limit of normal; W: Week; WD: withdrawal.

- a. Participants who discontinue JNJ-3989/placebo early will have an early WD visit, that should be scheduled as soon as possible, and will enter follow-up (as specified in Section 1.3.3) unless they withdraw consent. In case these participants continue in the follow-up phase, the follow-up visits can be scheduled based on WD visit date. Participants who withdraw consent will be offered an optional safety follow-up visit on the day of consent withdrawal. For the optional safety follow-up visit, assessments are at the investigator's discretion and could be similar to the early WD visit.
- b. If necessary (eg, for operational reasons), the screening phase may be extended up to a maximum of 8 weeks on a case-by-case basis and in agreement with the sponsor. Depending on the duration of the screening phase, selected screening assessments may have to be repeated prior to enrollment.
- c. Day 1 samples are to be collected before the first dose of study intervention.
- d. The ICF must be signed before the first study-related activity. Participants must sign a separate ICF if they agree to provide an optional DNA sample for pharmacogenomic research (where local regulations permit). Refusal to give consent for the optional DNA research sample does not exclude a participant from participation in the study.
- e. Minimum criteria for the availability of documentation supporting the eligibility criteria are described in the Source Documents section of Section 10.3, Appendix 3: Regulatory, Ethical, and Study Oversight Considerations. Clinical status will be checked at screening and again before first dose of study intervention. If a participant's clinical status changes (including any available laboratory results or receipt of additional medical records that becomes available during the screening phase) after screening but before the first dose of study intervention is given such that he or she no longer meets all eligibility criteria, then the participant should be excluded from participation in the study.
- f. Medical history also includes mode of HBV and HDV transmission and stage of liver fibrosis. Historical HDV RNA, anti-HDV antibodies, and HBV DNA to be reported in the CRF. HBsAg, HBeAg and ALT data, if available, to be recorded in source documents, but not in the CRF.
- g. Liver disease staging assessments will be performed based on FibroScan or liver biopsy results, obtained within 6 months prior to screening or at the time of screening (in case of FibroScan) or within 1 year prior to screening (in case of liver biopsy). If FibroScan is not available, acoustic radiation force impulse (ARFI) may be used if standard practice at the site or if otherwise validated and agreed with the sponsor (refer to Section 5.1, Inclusion Criteria for more information).
- h. Participants must have absence of signs of HCC or clinically relevant renal abnormalities on an abdominal ultrasound performed within 6 months prior to screening or at the time of screening. In case MRI monitoring is used per patient's standard of care, these MRI results may also be used. In case of suspicious findings on conventional ultrasound the participant may still be eligible if HCC or clinically relevant renal abnormalities has been ruled out by a more specific imaging procedure (contrast enhanced ultrasound, CT or MRI).
- i. HBV genotype will be determined at baseline using standard genotyping assay if HBV DNA levels are sufficiently high. For participants with low HBV DNA levels, available historical data on previous HBV genotype assessment will be collected in the CRF. Exploratory genotyping assays might be performed.
- j. HDV genotype may be determined by sequencing. For participants with low HDV RNA levels, available historical data on previous HDV genotype assessment will be collected in the CRF. Exploratory genotyping assays might be performed.
- k. For postmenopausal women only: an FSH level in the postmenopausal range may be used to confirm a postmenopausal state in women not using hormonal contraception or hormonal replacement therapy. However, in the absence of 12 months of amenorrhea, a single FSH measurement is insufficient to confirm a woman is not of childbearing potential.
- l. In between study visits, participants will take NA at home and they will bring their NA with them to each study visit.
- m. Complete physical examination, including height (at screening only), skin examination, and other body systems.
- n. A liver ultrasound is performed every 24 weeks from Day 1 for HCC screening in all participants. The liver ultrasound does not need to be repeated at baseline if it was done 3 months prior to screening or at time of screening. If a liver ultrasound is required at baseline, it can be performed between the Day 1 and the Week 2 visit (visit days included). For any subsequent liver ultrasound, a window of 1 week is allowed before or after the scheduled visit. In case MRI monitoring is used per patient's standard of care, these MRI results may also be used.
- o. Symptom-directed physical examination.

- p. Vital signs include supine SBP, DBP, pulse rate, body weight, and body temperature.
- q. All ECGs will be read centrally. Only on Day 1, the ECG will also be read locally prior to dosing to assess eligibility.
- r. All injection site reactions (ISRs; including ISRs below grade 1) will need to be recorded in the special events section of the CRF (see Section 8.3.6.2).
- s. Biochemistry samples must be taken after fasting for at least 10 hours for measurement of phosphate, calcium, creatinine, and lipids.
- t. Creatinine clearance (eGFR calculated by the CKD-EPI formula) will be assessed.
- u. Intervention-emergent ALT/AST elevations (ie, ALT and/or AST $\geq 3x$ ULN and $\geq 2x$ nadir [ie, lowest value during study participation]), should trigger an assessment of confounding factors (alcohol intake, change in concomitant medication, and comorbidities) and a confirmatory visit, to be scheduled preferably within 3 days of the receipt of the initial ALT/AST results, to repeat laboratory testing of AFP, ALT, AST, ALP, bilirubin (total and direct), INR, albumin, HBV DNA, and HDV RNA. Note that in case of urgency, local laboratory assessments could be considered (except for HDV RNA and HBsAg to protect the blind). Off-treatment local HDV RNA test can be done to exclude/assess for HDV driven flare. Additional tests should be considered based on clinical judgement. For more details and further management guidance refer to Section 8.3.6.1, Intervention-emergent ALT/AST Elevations and Section 10.6, Appendix 6: Intervention-emergent ALT/AST Elevations.
- v. Urine chemistry sample (quantitative measurement): creatinine, sodium, phosphate, glucose, protein, and albumin. Urinalysis by dipstick: specific gravity, pH, glucose, protein, blood, ketones, bilirubin, urobilinogen, nitrite, leukocyte esterase, and microscopic analysis if needed. In case of a positive dipstick result, a urine sample will be set aside for additional examination of the positive parameter at the central laboratory (eg, quantification as applicable).
- w. Urine sample for selected renal biomarkers including retinol binding protein and beta-2-microglobulin.
- x. A FibroScan assessment will only be done at baseline if it was not done at screening.
- y. Only applicable to participants who are enrolled at a site with access to a FibroScan device.
- z. At Week 52, participants of Arm 2 will switch to JNJ-3989 + NA, therefore, the FibroScan assessment at Week 48 is the baseline assessment for these participants.
- aa. For sites in the US, HDV RNA tests used to determine the participant's eligibility should be performed by a local laboratory.
- bb. HBcrAg and HBV RNA samples may be batched and only selected samples may be tested at the sponsor's discretion. Samples can be used for assessment of other serologic/virologic markers of HBV and HDV.
- cc. Sequencing at baseline (Day 1 predose) may be performed by default if HBV DNA levels and HDV RNA levels are within the ranges required for the sequencing assay; other samples may be sequenced upon the sponsor virologist's request. Samples might be used for exploratory analyses related to HBV/HDV or study intervention.
- dd. Quantitative HBeAg assessment will be performed throughout the study in participants who are HBeAg-positive at screening. In participants who are HBeAg-negative at screening, quantitative HBeAg testing should only be performed starting from the first qualitative HBeAg test result being positive.
- ee. Exploratory serology samples may be analyzed at the sponsor's discretion. Samples may be used to assess virologic or serologic markers of HBV/HDV including semi-quantitative anti-HDV IgM antibodies. These samples may also be used for host serum protein testing (eg, cytokines).
- ff. All participants will have sparse PK sampling. For all samples, the time of the preceding 2 intakes of NA and the time of PK sampling should be recorded. One sample at any time between 2 and 8 hours after JNJ-3989 dosing with collection of the time interval between last administration and blood draw. Before leaving the study site, the participant's well-being should be confirmed. In the event of special circumstances (eg, COVID-19 pandemic), the sample may be taken between 15 minutes to less than 2 hours postdose but the sponsor should approve first.
- gg. Antidrug antibodies samples should be collected prior to JNJ-3989 administration.
- hh. PBMC samples will be collected at selected sites only and as operationally feasible. Additional PBMC samples may be taken until Week 48 in case of ALT flares, upon discussion with the sponsor, which may require an unscheduled visit.
- ii. The pharmacogenomic (host DNA) sample is optional and will only be collected from participants who consent separately to this component of the study. The pharmacogenomic (host DNA) sample should preferably be collected at baseline.

- jj. The medical resource utilization data will include: (1) number and type of medical visits, (2) number (proportion) of participants requiring hospitalization and duration of hospitalization, and (3) number and character of diagnostic and therapeutic tests and procedures (inpatient and outpatient). For more details, refer to Section 8.9.
